#### Subject Identification, Recruitment and Consent

All consent procedures will be conducted by the research study personnel or the facility memory care representative who often has a personal relationship with residents and families. At this time, the informed consent document will be explained in detail and any questions will be answered. All participants will have a documented cognitive impairment and designated Legally Authorized Representatives. Because the designated Legally Authorized Representatives is required for the individual to live in a memory care facility, no participants will have capacity to consent independently. Legally Authorized Representatives will instead provide consent. If the individuals with dementia express any desire not to participate verbally or non-verbally to facility staff or Legally Authorized Representatives, they are instructed to alert research study personnel to remove the participate from the study.. If at any time, residents express verbal or nonverbal indication that they would like the camera removed, facility staff are instructed to place a cover over the camera and alert research study personnel at [name] or [[contact]](mailto:[contact]) to remove the resident from the study. Camera covers are provided in advance with more available as needed.

Subjects will not be compensated for participation in this study.

Subjects will not be charged for any of the study activities.

Inclusion criteria: residents included for this study are residents of memory care facilities who have agreed to participate in this clinical trial. All pilots have been conducted based on study design approved by the UC Berkeley IRB and the California Department of Social

Services Community Care Licensing Division. We have not selectively recruited or excluded ethnic (or other) minorities.

Exclusion criteria: (1) residents about to be transferred to a different facility where higher level of care is needed; (2) residents unable to consent and without Legally Authorized Representatives to provide consent, and (3) residents with Legally Authorized Representatives that choose not to take part. Compensation and measures to reduced dropouts:

Drop out: We do expect some residents to move to another location or pass away and have included the expected dropout based on the Phase I project into the statistical calculations used below to determine the necessary participant number.

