Data analysis: For aims 1, statistical analyses to address baseline comparison: Subjects' baseline characteristics (demographics and medical conditions) will be compared between the intervention and control groups using 2-sample t-tests (or appropriate nonparametric tests if the assumption of normality appears to be violated) and chi-square tests for continuous and categorical variables. Descriptive statistics will be used (means, frequencies, standard deviations, 95% confidence intervals) for all variables. We will examine the Aim #1a outcomes using a Poisson mixed-effects model to account for the nesting of outcomes within centers. We will account for baseline measures of resident activation and health status and resident demographics to statistically adjust for baseline imbalances, reduce residual intra-cluster correlation and improve the precision of estimated effects. Power analyses were performed via a simulation study in R version 3.4. and the lme4 package. We used 3 months of pilot data to guide and set assumptions for the data generating process. Based off initial data, we assumed centers ranged in size from 25-45 participants, and that roughly 30% of participants at each site would consent to the trial. Of those who consent, 50% will be randomized to the intervention. We fit the pilot data to a Poisson mixed effects model to obtain an estimate of the average monthly fall rate (0.49) as well as the between cluster variation in log fall rate ( $\sigma_{\text{twn}} = 0.467$ ). We generated 1000 sample data sets assuming different effect sizes (40%, 30%, 25% reduction in falls) and calculated the power obtained to detect this improvement due to intervention, as a function of the number of centers.

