Following the sample size for a time-averaged response methodology laid out in Fitzmaurice et al., we adjusted the total number of centers needed by a factor related to the number of observed months, anticipated participants per center (30% of 35 participants per center with 10% dropout) and the correlation between measurement months. The dropout rate was roughly at ~1% per month so a 10% dropout over 6 months is a conservative estimate. We assumed an extremely conservative estimate of the correlation between time points (months) of 0.8 and 6 months of follow-up. Reproducible R code is available at <https://github.com/[name]/>. We estimate that a total sample size of 460 ( $n=230/\text{arm}$ ) out of 19 facilities will be needed for a power of 80% to detect a 30% reduction in falls in the intervention group vs. control. Our approach of focusing on estimation and uncertainty and accepting the sample size collected for the main study, is congruent with experts' recommendations stating that the purpose of economic evaluation is not hypothesis testing; given there is no hypothesis testing, there is no requirement for a separate sample size calculation. For Aim 2, we will use similar descriptive statistics as described in Aim 1. For Aim 3, We will use a multivariate regression model to examine predictors of the main outcome, ER visits and hospitalizations (binary variable), using time to fall discovery by staff and time spent on the ground as the main predictors while controlling for baseline participant characteristics and facility characteristics.

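### The Aim 1 Poisson mixed model names no resident-level variance; fitted with a centre effect only, it understates the standard error of the arm effect to the extent that residents differ beyond the covariates

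*Combined protocol and SAP*

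**What the plan says.** Under Design, randomisation is by resident within each facility. Under Clinical outcomes, the Aim 1 outcome is the number of falls in facility incident reports. The Data analysis paragraph of that section analyses it "using a Poisson mixed-effects model to account for the nesting of outcomes within centers". It adds covariates: "We will account for baseline measures of resident activation and health status and resident demographics", partly to "reduce residual intra-cluster correlation and improve the precision of estimated effects". The pilot fit yields an average rate of 0.49 falls per month and one variance component, "the between cluster variation in log fall rate", with SD 0.467.

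The sizing text that follows brings in dependence over time: "we adjusted the total number of centers needed by a factor related to the number of observed months", together with participants per centre and dropout. It continues: "We assumed an extremely conservative estimate of the correlation between time points (months) of 0.8", with 6 months of follow-up. The result is 460 residents in 19 facilities, which "will be needed for a power of 80% to detect a 30% reduction in falls in the intervention group vs. control".

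No resident random effect, negative binomial or other overdispersion term, or robust variance appears anywhere in the document.

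**The concern.** With allocation within facility, the facility effect largely cancels from the arm comparison. The chance error that remains comes from differences between residents of the same facility. Given the facility and covariates, a Poisson model with only a centre effect sets the variance of a resident's count equal to its mean. If some residents fall persistently more often than others, the true variance is larger and the model does not see it.

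The primary p-value and confidence interval depend on this variance. If it is understated, a few frequent fallers landing by chance in one arm can produce a nominally significant difference. Sizing and analysis would also rest on different variances.

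**Working it through.** **Inputs from the document.** Control rate 0.49 per month, centre log-rate SD 0.467, rate ratio 0.70, power 80%, correlation 0.8, 6 months, 230 per arm. The document states no significance level; two-sided 5% is assumed.

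**1. The plan's sample size.** The time-averaged factor relative to six independent months is 1 + (6 − 1) × 0.8 = 5, or 5/6 relative to a single month. Then

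N = 2 × (1.96 + 0.8416)² × (1/m + 1/(0.7m)) / ln(0.7)² × (1 + 5ρ)/6.

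| Monthly mean m | N at ρ = 0.8 | N at ρ = 0 |
|---|---|---|
| 0.49 × exp(0.467²/2) = 0.5465 (0.49 as rate of the median facility) | 457 | 91 |
| 0.49 (as overall mean) | 510 | 102 |

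The 457 is before dropout; dividing by 0.9 gives 508. So 460 is matched closely only at m = 0.5465 with no dropout inflation. With six independent months, N stays near 100 (102/0.9 = 113 with dropout).

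**2. Can the centre effect supply the 0.8?** With A = exp(0.467²) − 1, the correlation between months due to centre alone is mA/(1 + mA) = 0.107 (m = 0.49) to 0.118 (m = 0.5465). It cannot.

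**3. Standard errors at the planning value.** 80% power at a rate ratio of 0.70 implies an SE of the log rate ratio of 0.3567/2.8016 = 0.127. A centre-only Poisson model at 230 per arm reports √(1/(230 × 6 × m) + 1/(230 × 6 × 0.7m)) = 0.0599 (m = 0.49) or 0.0567 (m = 0.5465), which is 2.1 to 2.2 times smaller.

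**4. Monthly or total counts.** With covariates constant over time, monthly Poisson counts and their 6-month sum give the same likelihood for the arm effect. Analysing totals does not remove the problem.

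**5. Type I error over an assumed range.** For resident log-rate SD s, after covariates, the variance factor is approximately F = 1 + 6m(exp(s²) − 1) and the error is 2Φ(−1.96/√F). This ignores the variation in rates between facilities. The simulation had 19 facilities, 12 residents per arm in each, 6 months, a centre random intercept and 1,000 null trials per row.

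| s (assumed) | F | Error by formula | Simulated, centre only | Simulated, resident-level robust SE |
|---|---|---|---|---|
| 0 | 1 | 5.0% | 5.4% | 6.5% |
| 0.25 | 1.19–1.21 | 7.2–7.5% | 6.1% | 4.8% |
| 0.50 | 1.84–1.93 | 14.8–15.8% | 18.3% | 4.4% |
| 0.75 | 3.22–3.48 | 27.5–29.3% | 30.7% | 6.9% |

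Across set-ups, the centre-only error was about 5% at 0, 6–10% at 0.25, 15–18% at 0.45–0.50 and 31–34% at 0.75.

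A further simulation (4,000 trials per row, 10% dropout, facility effects) used resident frailty with residual month-to-month correlation 0.1, 0.2 and 0.3. The frailty variance is φ = ρ/((1 − ρ) × 0.49) = 0.227, 0.510 and 0.875, so √ln(1 + φ) gives log-rate SDs of 0.45, 0.64 and 0.79. Type I error was 13.8%, 23.6% and 33.4%. If covariates absorb half the frailty it was 10.0%, 15.3% and 21.2%; with no residual correlation, 5.6%. Robust variance gave 4.4–5.9% throughout.

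**6. Effect on an interval.** In that simulation at a rate ratio of 0.70, the centre-only SE was 0.062, against true SDs of 0.079, 0.097 and 0.117. For an observed 0.70, the as-written 95% interval is 0.62–0.79. The matching honest intervals are 0.60–0.82, 0.58–0.85 and 0.56–0.88. Coverage of the as-written interval is 87%, 79% and 70%.

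**The case against.** The strongest reply is that the plan states a purpose for the mixed model, not a random-effects formula, and nowhere excludes a resident term. The R code it refers to did not come with the document and might contain one. That stands: a reader might infer that the plan rejects a resident term, and the text does not show this. But the sentence that defines the primary analysis names one level, and the choice moves the interval materially, so it cannot be left open.

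Second, the link to sizing is partly inference. The document speaks of correlation between months without saying within whom, and does not print the factor of 5. The match to 460 needs an assumed level and no dropout inflation, although the plan says dropout was included. A one-sided calculation with dropout and m = 0.49 gives 446, about as close. The 19 facilities are not reproduced either: 460/19 is 24.2 residents each, against a planned 30% of 35 = 10.5. All of this stands as a limit on how exactly the derivation is known. Even so, 446, 457, 508 and 510 all contain the 0.8 factor.

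Third, the covariates reduce the problem. They do, but only as far as they explain fall rates, and prior falls are not among the baseline items under Data collection.

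Fourth, at a residual SD of 0.25 the inflation is small. That is true, and the document offers no figure to show that the spread is that small.

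The remark in the sizing text that there is no hypothesis testing concerns economic evaluation. Aim 1 has a stated hypothesis and a power, and estimation needs a valid interval in any case.

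**Conclusion.** The point holds conditionally. Fitted as written, with a centre effect only, the Aim 1 model gives too small a standard error in proportion to the resident heterogeneity that the covariates leave unexplained. With none, it is valid. The error rates in the working rest on assumed residual spreads and a two-sided 5% level.

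Two stronger readings are not supported. A reader might infer that the standard error will be less than half its proper size, with a type I error of 36–41%. Those figures come from carrying the 0.8 into the analysis. The plan calls that value extremely conservative, so it is an upper extreme and not a forecast. A reader might also infer that the model fails whenever residents differ in fall rate; differences explained by the planned covariates do no harm.

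The point still needs correcting before analysis. It governs the primary interval, the error favours a false finding of benefit, and the plan's own sizing assumes strong dependence between months.

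**What to change.** State that the primary Aim 1 model carries resident-level variation, in one of two ways, and name one as primary in advance:

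- add a resident random intercept nested in facility to the planned Poisson mixed model, which is the smaller change; or
- use Poisson regression with arm, facility effects and the stated covariates, and resident-level robust (sandwich) variance, clustered on resident if months are the records.

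The simulations here tested the robust option; the random intercept was not simulated. In either case include log observed time as an offset, since the plan says "We do expect some residents to move to another location or pass away". Use a negative binomial mixed model with a facility random intercept as sensitivity analysis; its simulated type I error was 3.1–6.4%.

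The cost is wording and a standard variance method, with no new data. Confidence intervals widen. At N = 460 and a 30% reduction, simulated power with robust variance is 99.6%, 95.4% and 86.3% at residual frailty correlation 0.1, 0.2 and 0.3. It is 75–80% if the correlation really is 0.77–0.8 with monthly variance equal to the mean, so it may fall slightly short of the stated 80%.

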#### **Data collection:**

Demographic and clinical data set: We collect demographic data including age, gender, race/ethnicity, primary clinical diagnoses for SNF stay with specific focus on dementia subtype, most recent orthopedic surgery (<3 months) or reason for hospitalization, chronic medical conditions (top 3), and baseline medications (number of medications). Beyond the data collected from the video, data specific to the falls is collected either by direct extraction from the platform or from incident reports kept by facilities as (State regulations require facility track and file incident reports for all known falls). For the control population, the time of unwitnessed falls is unknown, but the number of falls and ER visits is collected from the existing facility incident reports. For the population equipped with SafelyYou Guardian, we will have direct access to the time of the fall, the time it took the HIL to verify the fall and call the facility, and the time on the ground. Note that for the residents with SafelyYou Guardian, we expect these values to be in increments of minutes.

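### The Aim 1 model adjusts for resident activation, which is never defined, and leaves out pre-enrolment falls, which sit in the same incident reports as the outcome: forgone precision, not a power shortfall

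*Combined protocol and SAP*

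**What the plan says.** The combined protocol and SAP covers this in three places.

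- **Adjustment** (Clinical outcomes section, Data analysis paragraph). Aim 1 uses a Poisson mixed model whose only named nesting is within centres. On covariates: "We will account for baseline measures of resident activation and health status and resident demographics". The stated reasons are chance imbalance, residual intra-cluster correlation and precision.
- **Baseline data** (Data collection section). The list runs from age, gender and race/ethnicity through diagnoses and recent surgery or reason for hospitalization, and ends with "chronic medical conditions (top 3), and baseline medications (number of medications". It contains no activation measure and no fall history.
- **Source of falls.** Data collection notes that "State regulations require facility track and file incident reports for all known falls". Clinical outcomes defines the Aim 1 primary outcome as falls found through that same routine incident reporting, in both arms.

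The planned baseline comparison covers demographics and medical conditions. No section says that falls before enrolment will be extracted, compared or modelled.

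**The concern.** A named covariate with no instrument, time point or source cannot be built from the plan alone. Someone would have to decide later what it means or drop it, possibly after outcomes are known.

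The omission matters more for efficiency. Fall counts usually vary widely between residents, and a resident's own earlier rate is the natural covariate to absorb that variation. For current residents it comes from the same record as the outcome, with the same fall definition and reporting habits. Without it, the treatment estimate varies more than it needs to, and a chance imbalance in fall history would not be seen in the planned baseline table.

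**Working it through.** **1. The plan's own figure.** The plan states that 460 residents (230 per arm) "will be needed for a power of 80% to detect a 30% reduction in falls in the intervention group vs. control". Inputs from the Data analysis text are "an estimate of the average monthly fall rate (0.49" per month), a standard deviation of 0.467 for the "between cluster variation in log fall rate", and a "correlation between time points (months) of 0.8 and 6 months of follow-up". Alpha is not stated; I assume 0.05 two-sided.

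- Centre-averaged control rate: 0.49 × exp(0.467²/2) = 0.546. Intervention rate: 0.7 × 0.546 = 0.383.
- One month: n per arm = (1.960 + 0.842)² × (1/0.546 + 1/0.383) / (ln 0.7)² = 274.2.
- Time-averaging factor: (1 + 5 × 0.8)/6 = 0.833. Then 274.2 × 0.833 = 228.5, so 229 per arm, or 458 in total.

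This matches 460 without dropout inflation. A one-sided test at rate 0.49 with 10% dropout gives 224 per arm, also within 3%. Each route needs a choice that the plan does not state. Neither takes credit for covariates.

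**2. Standard error (SE) from the centre-only Poisson model.** Expected falls over 6 months with 230 per arm:

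- Control: 230 × 6 × 0.546 = 754. Intervention: 0.7 × 754 = 528.
- SE of the log rate ratio = √(1/754 + 1/528) = 0.057.

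This depends almost only on the number of falls, so a covariate hardly changes it.

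**3. SE with resident variation.** Let φ be the variance of a resident frailty with mean 1. The documents do not give φ; I take 0.5 to 1.5. With month correlation = 0.49φ/(1 + 0.49φ), that range corresponds to 0.20 to 0.42, below the plan's 0.8. Approximately, SE = √(1/754 + 1/528 + 2φ/230):

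| φ | Approximate true SE, unadjusted | SE reported by centre-only model |
|---|---|---|
| 0.5 | 0.087 | 0.057 |
| 1.0 | 0.109 | 0.057 |
| 1.5 | 0.128 | 0.057 |

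Simulation gives about 0.09 to 0.15, somewhat higher because centres with high rates carry more weight.

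**4. Gain from prior falls.** Simulation settings: 460 residents, 19 facilities, rate 0.49, facility SD 0.467, rate ratio 0.70, six prior months, facility terms, robust errors, 1,200 replicates per cell. Variance of the log rate ratio, adjusted divided by unadjusted:

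| φ | Frailty correlation 0.6 | 0.75 | 0.9 |
|---|---|---|---|
| 0.5 | 0.90 | 0.84 | 0.73 |
| 1.0 | 0.85 | 0.75 | 0.56 |
| 1.5 | 0.82 | 0.66 | 0.52 |

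The cut is therefore 10% (1 − 0.90) to 48% (1 − 0.52). With a quarter of residents given a short look-back, the ratios were 0.57 to 0.91 at correlations 0.6 to 0.9, and 0.93 to 0.98 at 0.3.

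**5. Power with robust errors.** At φ = 1.5, power rises from about 77% to 85%–96%. At 1.0 it rises from about 87% to 92%–98%. At 0.5 it is already about 97% and reaches about 99%.

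**6. Form of the covariate.** The simple choice log((falls + 0.5)/months) fails for recent admissions. No falls in one week gives 0.5/0.25 = 2.0 per month, about four times 0.49, and zero months is undefined. With log((falls + 0.49)/(months + 1)), the rates inside the log are 0.49/1.25 = 0.39 for that resident, 0.49 at zero months, and 0.49/7 = 0.07 after six months without a fall.

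**The case against.** The strongest reply is that nothing here is an error. Randomisation within facility protects validity, adjustment for health status and demographics is already planned, and baseline health status could be read to include fall history. It is true that no stated target is missed. But the text does not say that fall history is included, and the baseline list omits it.

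Three further objections stand and limit the point.

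- **Not listed is weaker than not collected.** A reader might infer that activation is not collected and that the model cannot be fitted. The baseline list is introduced as including certain items, so the documents support only that activation is undefined and unlisted.
- **The planned model would not show the gain.** A reader might expect the reported interval to narrow once prior falls are added. Under the centre-only Poisson model it would not: the reported SE stays near 0.057, too small either way if residents differ as assumed.
- **The size is assumed.** Neither the frailty variance nor the prior-to-follow-up correlation is documented. At φ = 1.0, the variance ratio is 0.93 at correlation 0.45 and 0.99 at 0.3. The simulations in steps 4 and 5 of the working also take 460 residents, with no loss for the planned 10% dropout.

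**Conclusion.** The point holds as forgone precision. Resident activation needs a definition or deletion, and the plan omits a strong candidate covariate that its own data source contains. If frailty variance is 0.5 to 1.5, adjustment cuts the variance of the log rate ratio by about 10% to 48% at frailty correlations of 0.6 to 0.9, and by under 10% at 0.3. Power improves materially only at frailty variance of about 1.0 or more; at 0.5 the benefit is a narrower interval.

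Two stronger readings are not supported. One is that the trial falls short of 80% power for want of this covariate: the 460 takes no credit for covariates, so nothing in that calculation is lost. The other is that the plan's month-to-month correlation of 0.8 implies a variance cut of about 90%. That figure arises if frailty is unchanged from the prior to the follow-up period, and the plan itself calls 0.8 extremely conservative, so it is a ceiling and not an estimate.

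**What to change.** Make these changes before any outcome data are seen.

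1. **Data collection.** Add two baseline items from facility incident reports and admission dates: the number of reported falls in the 6 months before randomisation, and the months resident in that period.
2. **Data analysis, covariates.** Delete resident activation, or name its instrument, time point and source. Prespecify the prior fall rate as a covariate whatever the observed imbalance, in a form that is stable for short look-backs, such as log((prior falls + 0.49)/(prior months + 1)). This is defined at zero months and shrinks towards the planning rate of 0.49 per month.
3. **Data analysis, model.** Add a resident-level random effect, a negative binomial model or robust standard errors. Without one of these, the reported SE neither reflects resident variation nor shows the gain.

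The cost is a small extraction from existing records and a few sentences in the SAP. Recent admissions will contribute little information. The documents do not say whether consent covers extraction of pre-enrolment incident reports, so that must be confirmed.

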### Design

For Aim 1, we plan to recruit 460 study participants from 19 memory care facilities. For the purpose of this study, facilities will include Skilled Nursing Facilities (SNFs), or equivalent. Aim 1 will be a randomized controlled study using a waitlist control group. The randomization will occur at the individual (resident) level within each facility to control for variations at each facility in terms of facility size, facility administration, and staff training. During the first 6 months, n=230 will receive the intervention (SafelyYou Guardian, i.e. real-time alarms through a phone call from the HIL to the facility, front line staff intervention, and OT review), and n=230 will not receive the intervention. This design is the most rigorous way to test the intervention against the control: the randomization allows for control of confounding variables and has been previously used in the evaluation of medications, non-pharmacological, and mobile electronic interventions (where use of placebo treatment and blinding is not feasible) [87-89]. Previous work used a baseline as control, allowing possible confounding variables. As we recognize that 50% of the interested participants will not receive the intervention, those residents will be offered the intervention for a 6-month extension period (in order to accomplish Aim 2). This is the best compromise between the need for a rigorous randomized controlled trial vs. ethical responsibility to maximize benefit to each study participant.

For Aim #2, we will measure response times to each fall and the amount of time a resident spends on the ground after each fall. We intend to include all 460 participants' data from Aim #1. These will be participants who receive the initial intervention (n=230) and the additional participants who are on the waitlist control group who will receive the intervention in the second 6month period. The design for Aim #2 is observational in nature. The significance is that a large cohort of video data about the naturalistic progression of falls in residents with dementia has never been conducted to our knowledge. We will determine if the two time variables (time to fall discovery by staff and time spent on the ground after a fall, controlling

for baseline participant characteristics – i.e., demographics and medical conditions) and facility size, will predict need for ER visits or hospitalizations.

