#### Participant recruitment and retention

In the Phase I project, recruitment was performed by hosting a family night with care staff from the facility. Recruitment rate among families attending family nights was 85%. Our retention over 10 months with the 11 partner facility was near 100% (no family / resident ever requested to remove the system). One resident did begin taking the sign off the door after enrolling in the study, and the system was removed with approval from the family since he may have been attempting to object to the study. We credit this high retention to the very little burden required.

The recruitment of 460 residents will happen in batches (we expect to have access to our entire cohort 6 months from the start of the project). Once the resident population is recruited, we will deploy the system and onboard the facility staff. Onboarding will be gradual over 3 months. Through randomization, the population is split in half. One half, the control group, will not receive the intervention for the first 6 months, but will get the intervention for the next 6 months. The other half, the intervention group, will be in the study for the first 6 months only and then continue for the next 6 months. In total, 12 months will be needed per cohort. Installing the system requires 1-5 days depending on the facility size to mount the SafelyYou Guardian in the electrical closet alongside the router and PoE switches required to connect and power the cameras. Installation will be provided by SafelyYou contractor.

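### At the plan's own consent rate and centre size, 19 facilities would enrol about 200 residents, not the stated 460

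*Combined protocol and SAP*

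**What the plan says.** The Design section gives the target: "we plan to recruit 460 study participants from 19 memory care facilities", with 230 residents in each arm during the first 6 months. The sample-size statement, in the Data analysis paragraph under Clinical outcomes, repeats it: a total of 460 "out of 19 facilities will be needed for a power of 80% to detect a 30% reduction in falls".

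The same paragraph sets out the inputs:

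- Centre size: "we assumed centers ranged in size from 25-45 participants".
- Consent: "roughly 30% of participants at each site would consent to the trial".
- Allocation: "Of those who consent, 50% will be randomized to the intervention".
- Input to the adjustment of the number of centres: "anticipated participants per center (30% of 35 participants per center with 10% dropout".

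Under Subject Identification, Recruitment and Consent, the investigators say they "have included the expected dropout based on the Phase I project into the statistical calculations".

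Other uptake figures appear elsewhere. Participant recruitment and retention reports for Phase I that "Recruitment rate among families attending family nights was 85" per cent. The Privacy and security safeguards paragraph mentions 85–90% opting in to the system, 87 residents in 11 pilot facilities, and paid commitments for 480 beds. The sample-size text uses none of these.

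**The concern.** The plan gives its size in two units, residents and facilities, and at its own consent rate these describe trials of different size. This is the only sample-size justification for the randomised comparison in Aim 1. Power was computed as a function of the number of centres, and that number was then adjusted using participants per centre, so the facility count is an output of the calculation. It does not follow from the inputs shown.

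If recruitment is organised around 19 facilities and about 30% of residents consent, enrolment stops at less than half the target. A reader cannot tell which of the three figures to distrust.

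**Working it through.** **1. Yield from 19 facilities.** Inputs from the Data analysis paragraph: mean size 35 (midpoint of 25–45, and restated as 35), consent 30%, 10% dropout. Formula: facilities × residents per facility × consent.

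| Residents per facility | Enrolled | After 10% dropout | Shortfall in enrolment against 460 |
|---|---|---|---|
| 25 (all) | 19 × 25 × 0.30 = 142.5 | 128 | about 317 |
| 35 (mean) | 19 × 35 × 0.30 = 199.5 | 180 | about 260 |
| 45 (all) | 19 × 45 × 0.30 = 256.5 | 231 | about 203 |

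The rows for 25 and 45 are outer bounds. With sizes drawn uniformly from 25–45 and 30% consent, 100,000 simulated sets of 19 facilities enrolled 199 on average (95% range 172–228). None reached 460.

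**2. What 460 from 19 facilities implies.**

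- Per facility: 460/19 = 24.2.
- Consent needed: 24.2/35 = 69% (54% if all have 45 residents, 97% if all have 25).
- Residents per facility needed at 30% consent: 460/(0.30 × 19) = 80.7, against a stated maximum of 45.

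**3. Facilities needed at 30% consent.**

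- Mean size 35: 460/10.5 = 43.8, so 44.
- All at 45: 460/13.5 = 34.1, so 35. All at 25: 460/7.5 = 61.3, so 62.
- If 460 means completers, at mean size: 460/9.45 = 48.7, so 49.

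**4. Other readings tried.**

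- 10.5 taken as per arm gives 2 × 199.5 = 399 (359 after dropout). This misses 460 and contradicts the statement that half of those who consent go to the intervention.
- All centres at 45, 30% per arm, after dropout, gives 462. This needs the same contradicted reading and also contradicts the stated 35.
- Consent of 85% or 90% at 35 per facility gives 565 or 599.

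**5. Is 460 itself plausible as a power requirement?** The investigators' simulation code is not in the documents, so I used a closed form for a Poisson log rate ratio with a time-averaged factor:

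n per arm = (z_α + z_β)² × (1/λ + 1/(0.70λ)) / (ln 0.70)² × (1 + 5 × 0.8)/6

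The last factor is 0.833, from 6 months and the plan's correlation of 0.8. The monthly rate 0.49 can be read in two ways: as a model intercept, giving a marginal rate of 0.49 × exp(0.467²/2) = 0.546, with 0.467 read as a standard deviation; or directly as the marginal rate, 0.49. Alpha is not stated and is assumed.

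Total for 80% power:

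| Alpha 5% | Reading of 0.49 | No dropout loss | Dropouts contribute nothing (÷ 0.9) |
|---|---|---|---|
| Two-sided | Intercept | 2 × 228.5 = 457 | 508 |
| Two-sided | Marginal | 2 × 254.8 = 510 | 566 |
| One-sided | Intercept | 2 × 180.0 = 360 | 400 |
| One-sided | Marginal | 2 × 200.7 = 401 | 446 |

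The first row comes close to the plan's 460, with no allowance for dropout.

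**6. Power for a 30% reduction, same formula (intercept / marginal).**

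| Residents per arm | Two-sided 5% | One-sided 5% |
|---|---|---|
| 99.75 (19 facilities, 30% consent) | 45.7% / 41.8% | 58.2% / 54.3% |
| 89.8 (same, dropouts contribute nothing) | 41.9% / 38.3% | 54.4% / 50.7% |
| 230 (the stated total) | 80.3% / 75.9% | 87.8% / 84.5% |
| 207 (same, dropouts contribute nothing) | 76.0% / 71.4% | 84.7% / 81.1% |

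**The case against.** The best reply concedes the yield and disputes the consequence. Randomisation is to individuals within facilities, and in the closed form above the facility count does not affect power at a fixed total. Participant recruitment and retention speaks of enrolling 460 residents in batches and names no facility count there. If 460 are enrolled from however many sites, one reading gives about 80% power, and the error is one of site count and feasibility. That is fair. The low power applies only if recruitment ends at 19 facilities with 30% consent.

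The power figures are also only indicative:

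- They use the correlation of 0.8, which the plan itself calls extremely conservative. At 99.75 per arm and two-sided 5%, illustrative correlations of 0.5 and 0.3 give 60% / 55% and 75% / 70% (intercept / marginal).
- The plan's adjustment factor also involves participants per centre, which the closed form omits.
- If 0.467 were a variance, the two-sided total without dropout loss would be 404 in place of 457, and power at 99.75 per arm about 50%.

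Dropout is not wholly unexplained either. It enters through participants per centre when the number of centres is adjusted. What is not said is how it is reflected in the total of 460.

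None of this touches the contradiction, which needs only multiplication of stated inputs. The higher uptake figures do not resolve it: they concern families who attended a family night, or opting in to the system, and at 35 residents per facility they overshoot 460.

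**Conclusion.** The concern holds. Nineteen facilities, 30% consent and 460 residents cannot all be true for any centre size from 25 to 45. At the mean, 19 facilities enrol about 200, a shortfall of about 260. This part is exact and depends on no assumption about alpha, fall rate or correlation.

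What follows depends on which figure gives way:

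- 30% and 460 stand: about 44 facilities.
- 19 and 460 stand: about 69% consent at mean size.
- 19 and 30% stand: about 200 residents, with power of about 38–46% at two-sided 5% or 51–58% at one-sided 5%. These are approximate, at the plan's correlation of 0.8 and with 0.467 read as a standard deviation.

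The documents do not show which figure is wrong. The total of 460 is plausible on one reading but not verified. As written, the facility count does not follow from its inputs and the 80% power cannot be confirmed. This must be corrected, because the sizing of the primary comparison rests on it.

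**What to change.** 1. State one consent rate and its basis, and make consent rate, residents per facility, facility count and total agree in the Design section and the Data analysis paragraph. If 30% and 460 stand, restate the facility count as about 44 at mean size 35. If 19 and 30% stand, restate expected enrolment as about 200 and lower the stated power. If a higher consent rate is justified, correct the 30% and explain why it departs from the initial data.
2. Rerun the existing simulation at the reconciled inputs. State alpha, whether 0.49 is an intercept or a marginal rate, and whether 460 counts residents enrolled or completing, then restate the power.

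The cost in every case is a rerun of existing R code and rewording of two sections. The rerun is needed even if only the consent rate changes, because participants per centre feeds the adjustment. If 30% and 460 both stand, finding about 25 more facilities (44 − 19) is a real cost, better known before recruitment than discovered during it.
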